5.2 Inclusion criteria

The trial entry criteria will be based on a diagnosis of 'definite' NASH on liver biopsy obtained within 6 months of screening. Throughout the study, all liver biopsies will be read centrally by one single (RP) expertised pathologist from the central trial site (HUMANITAS Gradenigo), blinded to clinical and laboratory data and to treatment allocation: prior to randomisation, the liver histopathologist will review all of the liver biopsies of the potential participants to assess whether a diagnosis of 'definite' NASH is present.

A 'definite' diagnosis of NASH is defined if all of the following are present on biopsy: (1) macrovesicular steatosis (>5%); (2) hepatocyte ballooning (\pm Mallory Hyaline) and (3) lobular inflammation (mixed infiltrate, related to foci of ballooning). Only patients with 'definite' NASH will be classified as eligible. All participants are to be ≥ 18 to <70 years of age and have a BMI ≥ 25 kg/m² at screening. Patients with type 2 diabetes mellitus (T2DM) at screening had to have stable glycaemic control (HbA1c <9%) and be managed by either diet and/or a stable dose of metformin/sulfonylurea/s. Patients without a history of T2D prior to the screening visit will undergo a 75-g standard OGTT and/or have their HbA1c measured at screening to determine their glycaemic status and will be labelled as 'non-diabetic' if one or more of the following was confirmed

- Impaired fasting glucose, defined using the European Criteria between 110 and 126 mg/dL.
- IGT, defined as 2 h plasma glucose levels between 140 and 200 mg/dL on the 75 g OGTT.
- Normal Fasting Plasma Glucose <110 mg/dL and normal 2 h plasma glucose levels <140 on the 75 g OGTT.
- HbA1c <6.5%

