5.3 Exclusion criteria

A detailed summary of the exclusion criteria is provided in **box 1**. In brief, patients with a history or current significant alcohol consumption, poor glycaemic control (HbA1c >9.0%), Child's Pugh B or C cirrhosis or other liver disease aetiology were excluded. The latter was confirmed with a full liver aetiology screen (drug induced, viral hepatitis B/C, autoimmune and genetic) at the screening visit. Past and current alcohol consumption was ascertained by a detailed review of the patient's medical, social history and by a validated, self-administered food frequency questionnaire with reference pictures to remind participants of drink equivalents (see dietary record section). Concomitant use of drugs reported to be inducers (methotrexate, amiodarone, steroids) or potential therapies for NASH (TZDs, GLP-1 analogues, vitamin E), or other known hepatotoxins were assessed during the screening visit (**box 1**).

Box 1. Exclusion criteria

1. Refusal or lacks capacity to give informed consent to participate in the trial.
2. Participation in any clinical trial of an investigational therapy or agent within 12 months of randomisation.
3. Patient (or carer) deemed not competent at using the correct site and technique for subcutaneous injection of the trial treatment (containing dummy drug on practice).
4. NAFLD Activity Score (NAS) <3 on liver biopsy.
5. Child's B or C cirrhosis or clinical evidence of decompensated chronic liver disease: radiological or clinical evidence of ascites, current or previous hepatic encephalopathy and evidence of portal hypertensive haemorrhage or varices on endoscopy.
6. Medical history of multiple drug allergies (defined as anaphylactoid drug reactions in >2 drug groups) or allergy to curry or curcumin-based nutraceuticals
7. Presence of any acute/chronic infections or illness that at the discretion of the chief investigator might compromise the patient's health and safety in the trial.
8. Pregnancy or breastfeeding.
9. Women, of childbearing age, who are not willing to practise effective contraception (ie, barrier, oral contraceptives, impenon or past medical history of hysterectomy) for the 48-week duration of the trial and for 1 month after the last administration of the drug.
10. Liver disease of other aetiologies (ie, drug-induced, viral hepatitis, autoimmune hepatitis, PBC, PSC, haemochromatosis, A1AT deficiency, Wilsons disease).

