5.5 Randomization, stratification and blinding

Randomization and stratification

Participants meeting all the eligibility criteria and providing written informed consent will be randomized centrally on a 1:1 basis to either of the two-study treatments (phytosomal curcumin vs placebo) using computer generated randomization. To ensure even distribution between groups in key baseline covariates, randomization will be stratified into blocks of 4 according to the following variables: diabetes status (present vs. absent), obesity status (present vs. absent), fibrosis stage (stage F3-4 vs. stage 0-2), CKD (present vs. absent). Trial participants will be allocated a unique trial identification number to preserve patient confidentiality and enable the study to be double-blinded. Patients, investigators, assessors, trial site staff, and the sponsor (except for specific laboratory staff and individuals responsible for safety) remained blinded to treatment assignment throughout the trial.

Medication preparation and blinding/unblinding procedures

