Histological NASH resolution (defined by the NASH Clinical Research Network as no more than mild residual inflammatory cells [score of 0 or 1] and no hepatocyte ballooning [score of 0]) **and** no worsening of liver fibrosis (with worsening defined as an increase of one stage or more on the Kleiner fibrosis classification scale) after 72 weeks, in line with regulatory perspectives^{31,32}.

Secondary outcome measures

Liver-centered histological outcomes:

1) a ≥ 1 stage improvement in fibrosis and no worsening of NASH (with worsening defined as an increase of ≥ 1 point in either the lobular inflammation score or the hepatocyte ballooning score according to the NASH Clinical Research Network criteria) after 72 weeks

2) improvement in clinically significant fibrosis³³, defined by the proportion of patients with baseline fibrosis stage ≥ 2 who have fibrosis stage 0-1 at EOT, without worsening of NASH.

3) improvement in advanced fibrosis, defined by the proportion of patients with baseline fibrosis stage 3-4 who have fibrosis stage 0-2 at EOT, without worsening of NASH.

3) a ≥ 2 -point improvement in NAFLD activity score (NAS), with at least 1 point improvement in either ballooning or lobular inflammation score;

4) individual components of the NAFLD activity score (steatosis, hepatocyte ballooning, lobular inflammation) and the Kleiner fibrosis stage. Fibrosis stages 1a, 1b, and 1c were considered stage 1 for the purposes of analysis.

Liver-centered non-histological outcomes:

4) changes from baseline to 72 weeks in serum liver enzyme concentrations, improvement in noninvasive markers of liver disease severity, including computerized sonographic hepato-renal ratio (which correlates closely with histologic and ¹H magnetic resonance spectroscopy steatosis^{34,35, 36,37,38}, see **Analytical**

Methods subheading), serum cytokeratin-18 fragments(a marker of NASH), NAFLD fibrosis score, FIB-4 and serum lumican (as markers of fibrosis)(see supplementary material).

The extracellular matrix proteoglycan lumican was chosen because its circulating levels have been shown to be a reliable marker not only of hepatic fibrosis but also of active hepatic fibrosis deposition, its expression is upregulated by Nf-kB, and its levels have been shown to differentiate histologically progressive, fibrosing NASH from mild, nonprogressive NAFLD^{39, 40, 41}

Non liver-centered outcomes

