8.1 Liver histopathology and immunohistochemistry

8.1.1 Liver histopathology

One liver histopathologist (RP) with specific expertise in NAFLD, blinded to the clinical, laboratory and study treatment allocation, will perform all the histopathological assessments at the central trial site (HUMANITAS Gradenigo) using an in-house designed proforma. The histological diagnosis of NASH will be established using H&E staining and haematoxylin van Gieson stains of formalin-fixed paraffin-embedded liver tissue. Both the baseline and end-of-treatment (72 weeks) biopsies will be reported as either 'definite NASH,' 'uncertain NASH' or 'not NASH.' The histological diagnosis of 'definite NASH' is defined as a combination of >5% macrovesicular steatosis, hepatocyte ballooning (\pm Mallory's Hyaline) and lobular inflammation (mixed infiltrate, related to foci of ballooning)⁴⁶. The assessment of ballooning is subjective, and thus for 'uncertain' hepatocyte ballooning, a key component of the diagnosis of NASH, ubiquitin immunohistochemistry will be used to identify material compatible with Mallory's hyaline.

To validate the quality of the biopsy specimen, the core specimen length will be measured and the number of portal tracts will be recorded.

The NAS will be calculated based on the Kleiner classification⁴⁷ The NAS is scored of 8, with 8 representing the highest activity. The NAS is the sum of scores of the 3 components of the histological scoring system, namely steatosis (0= \leq 5%, 1=5–33%, 2= \geq 33–66%, 3= \geq 66%), lobular inflammation (0=no foci, 1= \leq 2 foci/ \times 200, 2=2–4 foci/ \times 200, 3= \geq 4 foci) and hepatocyte ballooning (0=none, 1=few ballooned cells, 2=many cells/prominent ballooning). The Kleiner scoring system for NAFLD fibrosis (F0-F4) will be used to evaluate the stage of fibrosis in each biopsy specimen. Portal tract changes (inflammation, interface hepatitis, ductular reaction), an intrinsic feature of NASH, will also be recorded⁴⁸. The pathologists will score each histological feature of liver biopsies and fill in separate forms.

8.1.2 Potential relevance of Nuclear Factor κ B (NF- κ B) activation in the liver and mononuclear cells (MNCs) for NASH pathogenesis and curcumin treatment

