9.2 Methods for analysis of primary and secondary outcomes

All evaluable patients will be analysed on an intention-to-treat basis. Evaluable patients are defined as those who have had an end-of-treatment biopsy, irrespective of the amount of treatment they have received.

Patients will be categorised as either achieving the primary histological endpoint (ie, NASH resolution) or not. The proportion of patients with a reported improvement in liver histology will be presented and compared across treatments descriptively with 95% CIs.

The primary analysis will be based on a Cochran–Mantel–Haenszel test based on all randomised patients for the in-trial period with missing data handled as non-responders. The common risk ratio between phytosomal curcumin and placebo was estimated along with exact 95% CI. To test for superiority, the exact two-sided p-value was calculated as the sum of probabilities of outcomes having equal or lower probability than the observed outcome under the null hypothesis.

Adjustments for multiplicity testing in the primary analysis will be performed with the use of the Benjamini-Hochberg procedure; each active-treatment group was compared with the placebo group. Two-sided P values <0.05 were considered statistically significant.

An unpowered, preplanned secondary analysis of categorical outcome measures will be done using the χ^2 test or Fisher exact test, as appropriate, of the difference between the proportions of patients with histological improvement in each treatment group.

A preplanned logistic regression analysis will be undertaken to determine the treatment effect when adjusted for the stratification variables (diabetes status, obesity status, fibrosis stage, CKD status) and trial site. We will calculate adjusted relative risks using the Mantel-Haenszel test. Two-sided P values <0.05 will be considered statistically significant in all analyses.

Continuous secondary outcome measures will be compared between treatment groups using linear

regression, adjusting for parameter baseline values and allocated treatment (as model covariates, equivalent to ANCOVA), with multilevel modelling for key continuous outcome measures to account for repeated measures within each patient.

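### Baseline ballooning and inflammation grades are on file before randomisation but are used in neither the primary CMH test nor the preplanned logistic model, so some efficiency and protection against chance imbalance is lost

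*Protocol*

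**What the plan says.** Protocol section 7 (Primary outcome measure) defines resolution as "no more than mild residual inflammatory cells [score of 0 or 1] and no hepatocyte ballooning [score of 0", together with no worsening of fibrosis at week 72. Section 5.2 requires steatosis, ballooning and lobular inflammation all to be present at entry, and Box 1 in section 5.3 excludes "NAFLD Activity Score (NAS) <3 on liver biopsy".

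The grades exist for every patient. Section 5.2 says that "prior to randomisation, the liver histopathologist will review all of the liver biopsies of the potential participants", and section 8.1.1 that "The pathologists will score each histological feature of liver biopsies and fill in separate forms".

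Randomisation (section 5.5) is stratified by "diabetes status (present vs. absent), obesity status (present vs. absent), fibrosis stage (stage F3-4 vs. stage 0-2), CKD (present vs. absent". In section 9.2, "The primary analysis will be based on a Cochran–Mantel–Haenszel test based on all randomised patients for the in-trial period with missing data handled as non-responders"; no strata are named. The preplanned logistic model is "adjusted for the stratification variables (diabetes status, obesity status, fibrosis stage, CKD status) and trial site". The reference-based imputation in section 9.5 matches on the same four factors. Baseline ballooning, inflammation or NAS appears in none of these. Continuous secondary outcomes, by contrast, are analysed "adjusting for parameter baseline values and allocated treatment (as model covariates, equivalent to ANCOVA".

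**The concern.** On the section 8.1.1 scales (ballooning 0–2, inflammation 0–3), eligible patients start at very different distances from response. One who enters at ballooning 1 and inflammation 1, with steatosis 1, has NAS 3 and needs a single grade of ballooning to go; the inflammation part is already met. One who enters at ballooning 2 and inflammation 3 needs two grades of each, four in all. That difference follows from the endpoint definition and needs no outside evidence.

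With 52 patients randomised 1:1, baseline activity can differ between arms by chance, and no stated analysis takes account of it. The between-arm test also has little power to spare, so leaving an available baseline measure unused may matter.

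**Working it through.** **The plan's own figure.** Section 9.1 gives at least 8 responders of 21 (A'Hern, alpha 0.05, power 0.90). For X binomial with n = 21, P(X ≥ 8) = 0.043 at a 20% response rate and 0.905 at 50%, so the rule reproduces with 20% versus 50%. The text itself cites 15% for lifestyle intervention. Both control rates are used below.

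**Power of the planned comparison.** By the two-proportion formula with 26 per arm and two-sided 0.05, power is 0.79 for 15% versus 50% and 0.47 for 15% versus 38%. The 38% is the 8/21 threshold.

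**Chance imbalance (assumption: half the patients have high baseline grades).** Taking two independent Binomial(26, 0.5) counts, the arms differ by at least 5 patients (5/26 = 19 points) with probability 0.21, and by at least 6 (23 points) with probability 0.13. With control response 15% overall:
- odds ratio 4 (low versus high activity) means 23% versus 7%; a 20-point imbalance shifts the risk difference by 0.20 × 0.16 = 3 points
- odds ratio 8 means 26% versus 4%; the shift is 0.20 × 0.216 = 4 points

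**Effect of stratifying the CMH test.** Simulation of 40,000 trials per row: 26 per arm, two-level activity factor at 50% prevalence, assumed prognostic odds ratio (OR) of 1, 2, 4 or 8, intercepts set so that each arm keeps its marginal response rate. The asymptotic CMH test has no continuity correction. The exact test uses the section 9.2 rule (sum of outcomes no more probable than the one observed), applied to the conditional distribution of curcumin responders. Monte Carlo error is about 0.2 points per figure.

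| Rates | OR | Asymptotic: without → with (%) | Exact: without → with (%) |
|---|---|---|---|
| 15 v 50 | 1 | 78.9 → 78.4 (−0.5) | 70.3 → 73.0 (+2.7) |
| | 2 | 79.0 → 79.5 (+0.5) | 70.6 → 74.3 (+3.7) |
| | 4 | 79.6 → 82.3 (+2.7) | 70.9 → 77.3 (+6.4) |
| | 8 | 79.0 → 85.2 (+6.2) | 70.3 → 80.1 (+9.8) |
| 20 v 50 | 1 | 63.0 → 62.6 (−0.4) | 53.6 → 56.6 (+3.0) |
| | 2 | 62.8 → 63.5 (+0.7) | 53.4 → 57.4 (+4.0) |
| | 4 | 63.0 → 66.7 (+3.7) | 53.6 → 60.3 (+6.7) |
| | 8 | 63.2 → 70.9 (+7.7) | 53.8 → 64.5 (+10.7) |

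The exact test gains about 3 points even at OR 1, where the factor carries no information. That part comes only from reduced discreteness.

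**Type I error.** With equal rates of 15% or 20% in both arms, rejection was 4.7–5.3% (asymptotic) and 2.0–2.3% (exact) without the factor, and 4.7–5.2% and 2.7–3.1% with it.

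**How far the remedy can go.** A separate simulation of the asymptotic CMH test at 15% versus 50% and OR 4, with blocks of 4 in 16 cells, gave power of 0.78 unstratified, 0.81 by activity alone, 0.73 by the 16 randomisation cells, and 0.59 by the 16 cells crossed with activity.

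For the logistic model, expected responders at 15% versus 50% are 26 × 0.15 + 26 × 0.50 = 17. Under the null at 15% in both arms they are 52 × 0.15 = 8. There, the likelihood-ratio test of treatment had type I error of about 0.09 with the five listed covariates and 0.11–0.13 once both grades were added.

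**The case against.** **Silence is not exclusion.** The CMH strata could be named in a statistical analysis plan that is not shown. This stands: the protocol cannot be said to rule the grades out of the primary test. It does fix the logistic covariates and the imputation matching factors, and leaves the grades out of both.

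**The planned analysis is conventional and valid.** This also stands. A reader might infer that the primary test is biased or its error rate wrong. The simulation does not support that: the test without the factor holds its level, and a shift of 3 to 4 points sits inside a standard error of √((0.15×0.85 + 0.50×0.50)/26) = 12 points that already allows for chance imbalance.

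**The contrast with continuous outcomes is not a contradiction.** A reader might say that the primary outcome is denied adjustment for its own baseline value. But the endpoint is binary and ballooning must be present at entry, so every patient is unresolved at baseline. The grades are prognostic factors, not a baseline value of that endpoint.

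**The gain is assumed.** The protocol gives neither the prognostic strength nor the distribution of the grades. A reader might apply the continuous-outcome variance factor (1 − ρ²) with ρ = 0.5 and infer larger gains. With a 50/50 factor, the correlation is greatest when all control responders have low activity: 0.40 × 0.5/√(0.20×0.80) = 0.50 at 20% response, and 0.30 × 0.5/√(0.15×0.85) = 0.42 at 15%. So 0.5 is the ceiling in one case and out of reach in the other, and no weight should be put on such figures.

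**Conclusion.** The point holds as one of efficiency and robustness, not validity. Grades that determine the distance to the primary endpoint are recorded before randomisation and are used in no stated primary or adjusted analysis.

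The gain in asymptotic power from one activity stratum is about 0, +0.5, +3 to 4 and +6 to 8 points at assumed odds ratios of 1, 2, 4 and 8, so it is small if activity is only weakly prognostic. The exact test gains 3 to 11 points, of which about 3 are reduced discreteness. These figures rest on 26 per arm, a 50/50 split, 50% response with curcumin, and 15% or 20% with placebo. The change is worth making because it uses data already collected and costs almost nothing if the assumption of prognostic value fails.

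**What to change.** In section 9.2:
- Name one two-level baseline activity factor as the stratum of the primary CMH test, built from the endpoint's own components, for example ballooning grade 1 versus 2. A cut on total NAS is less suitable because it includes steatosis, which is not part of resolution.
- Fix the cut-point before unblinding. The pooled, blinded baseline grades can show whether both levels hold enough patients.
- Do not cross this factor with all 16 randomisation cells.
- In the logistic model, use the same single factor in place of a weaker term, or keep the list and fit a penalised or exact model. Do not add both grades to the existing five covariates.

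The cost is a few sentences and no new data. If baseline activity is unrelated to resolution, asymptotic power falls by about half a point (−0.4 to −0.5 in the table). Dropping a listed term from the logistic model gives up adjustment for that term, so the choice should be stated in advance.

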5.1 Eligibility criteria

Eligible adult patients (≥ 18 years old) were identified and recruited at the participating trial site centres starting in August 2018 and ending by June 2022, 52 patients will be recruited. Participating trial centres will include the Liver and Metabolic Units at the Humanitas Gradenigo Hospital (Turin) since August 2018), and the Metabolic Unit of Dept of Medical Sciences at the Città della Salute e della Scienza hospital (Turin) since Sept 2018).

All trial participants will give informed written consent at the beginning of the screening visit prior to undergoing any tests and procedures needed to assess eligibility.

Eligibility for the trial will be determined at screening visit 1 by standard blood tests, clinical history (including written-confirmation of drug history where necessary) and physical examination to identify other illnesses or contraindications for participation.

Patients who satisfied the eligibility criteria trial at both sites will be offered to take part in a metabolic mechanistic substudy. The substudy involves a standard Oral Glucose tolerance Test (OGTT) and a standard Oral Fat Tolerance Test (OFTT) on three admissions (at least 24 hours apart from each other) and an indirect calorimetry test at the two participating centres on visits 2 (pretreatment) and 8 (4 weeks

post-treatment). A detailed summary of the metabolic substudy will be published separately. A patient's decision to partake or withdraw from the metabolic substudy will not affect their participation in the main 72-week trial.

A schematic view of trial schedule and design is presented in **Figure 1**.

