9.1 Power analysis

Sample size justification. There are no data on liver histological response to curcumin.

The sample size was calculated using A'Hern's single stage phase II methodology⁷⁷ with a significance level of 0.05 (type I error) and power of 0.90 (type II error).

Based on previous trials showing an improvement in surrogate markers of NAFLD with curcumin ranging 20- 50% of patients, depending on different liver disease surrogates, curcumin dose, formulations and treatment duration vs. 15% with lifestyle intervention⁷⁸, the design required 21 evaluable patients in the phytosomal curcumin group; after allowing for a 10% dropout rate, at least 25 subjects per arm were needed to detect a significant difference in the primary outcome. The study A'Hern's design stipulates that at least eight (38%) out of 21 patients in the phytosomal curcumin group have to achieve histological improvement for phytosomal curcumin to be deemed worthy of further investigation with a phase III trial⁸⁴

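### The general models for continuous secondary outcomes leave out the four randomisation factors, which costs precision if those factors predict outcome beyond the baseline value

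*Protocol*

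**What the plan says.** Section 5.5 (Randomization, stratification and blinding) states that "randomization will be stratified into blocks of 4 according to the following variables: diabetes status (present vs. absent), obesity status (present vs. absent), fibrosis stage", the last of these split as F3-4 against 0-2, with CKD as a fourth binary factor. Patients are "randomized centrally on a 1:1 basis to either of the two-study treatments", and section 5.1 plans that "52 patients will be recruited".

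Section 9.2 sets out the analyses:

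- **Continuous secondary outcomes:** linear "regression, adjusting for parameter baseline values and allocated treatment (as model covariates, equivalent to ANCOVA), with multilevel modelling for key continuous outcome measures". The covariates named are the baseline value and treatment.
- **Categorical outcomes:** "An unpowered, preplanned secondary analysis of categorical outcome measures will be done using the χ^2 test or Fisher exact test, as appropriate". The next paragraph preplans a logistic regression adjusted for all four stratification variables and trial site, with Mantel-Haenszel adjusted relative risks. It does not say which binary outcomes these cover.
- **eGFR slope:** a separate mixed model. Section 9.2 lists diabetes and CKD stage among its covariates; section 7 lists diabetes and baseline fibrosis stage. Neither list includes obesity.
- **Significance:** "Two-sided P values <0.05 will be considered statistically significant in all analyses".

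The sensitivity analysis for missing data (section 9.5 in the text) matches imputation donors on the same four factors.

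**The concern.** Stratifying on a prognostic factor makes the arms more alike on it, which reduces the true sampling error of the treatment difference. A model without that factor does not register the gain. The factor's variance stays in the residual, so the standard error is larger than the estimate's actual variability. Tests then run below the nominal 5% and intervals are wider than they need to be. Any imbalance left by incomplete blocks also goes uncorrected.

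The protocol uses the four factors in the adjusted logistic regression and in the imputation, but gives no reason for leaving them out of the general continuous model. That model serves liver enzymes, cytokeratin-18 fragments, FIB-4, the NAFLD fibrosis score, lumican, anthropometry, glucose, HbA1c, lipids and inflammatory markers. Several of these carry the key secondary hypotheses in section 2. In a trial of 52 patients, precision is worth keeping.

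**Working it through.** **The plan's own figure.** The protocol gives no power statement for continuous secondary outcomes. Its only design figure is the A'Hern rule for the primary outcome in section 9.1: at least 8 responders among 21. Taking response rates of 20% (null) and 50% (target), the ends of the range quoted there, an exact binomial search returns n = 21 and r = 8, with type I error 0.043 and power 0.905. That rule does not involve the continuous models, so this point leaves the sample size unchanged.

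**Inputs from the protocol.** N = 52; 1:1 allocation; blocks of 4; 2 × 2 × 2 × 2 = 16 strata; two-sided 5% tests. The mean stratum size is 52/16 = 3.25, below the block size. Many blocks therefore stay incomplete and balance is only partial; the simulation includes this.

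**Assumptions, not in the protocol.** Factor prevalences of 50%, 50%, 30% and 35%; a true effect of 0.8 SD of the variation left after baseline; and R², the share of that variation explained by the four factors, from 0 to 0.30.

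**Models compared.** As written: intercept, treatment, baseline value (52 − 3 = 49 residual degrees of freedom). Adjusted: the same plus four main effects (52 − 7 = 45). There were 6,000 simulated trials per setting. The Monte Carlo standard error is √(0.05 × 0.95/6000) ≈ 0.3 points for type I error and √(0.8 × 0.2/6000) ≈ 0.5 points for power.

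| R² | Type I error, as written / adjusted | Power, as written / adjusted | Ratio of interval widths (as written ÷ adjusted) |
|---|---|---|---|
| 0 | 4.9% / 5.1% | 80.6% / 79.5% | 0.98 |
| 0.05 | 4.9% / 5.0% | 79.3% / 80.4% | 1.01 |
| 0.10 | 4.6% / 5.4% | 80.2% / 82.2% | 1.04 |
| 0.20 | 3.5% / 5.3% | 80.7% / 86.3% | 1.10 |
| 0.30 | 3.1% / 4.9% | 81.9% / 91.0% | 1.18 |

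**Hand check on the widths.** Removing a share R² of the residual variance should change the ratio by 1/√(1 − R²). Starting from the simulated 0.984 at R² = 0:

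- R² = 0.10: 0.984 × 1.054 = 1.04
- R² = 0.20: 0.984 × 1.118 = 1.10
- R² = 0.30: 0.984 × 1.195 = 1.18

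All agree with the table.

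**With 10% of outcomes missing.** Two repeats under the same allocation scheme gave, as written vs adjusted:

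- R² = 0: power 75% vs 73% in both
- R² = 0.10: 75% vs 77%, and 75% vs 76%
- R² = 0.20: 76% vs 82%, and 78% vs 82%
- R² = 0.30: 78% vs 87%, and 77% vs 87%

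Type I error as written was 3.8% and 4.1% at R² = 0.20, and 3.0% and 2.9% at R² = 0.30.

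**Where the loss arises.** In the first repeat at R² = 0.30, the mean model standard error as written was 0.296 against a true SD of 0.268 (ratio 1.10). After adjustment the figures were 0.252 and 0.253 (ratio 1.00). About 10% is overstatement of the standard error. A further 0.268/0.253 = 1.06 is real imprecision from imbalance that adjustment would remove.

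These runs cover the single-time-point ANCOVA. The same reasoning applies to between-patient variance in the multilevel models, but its size there was not calculated.

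**The case against.** **The loss depends on an unstated R².** What counts is what the factors explain after the baseline value is in the model. For HbA1c and diabetes, or weight and obesity, the baseline measurement may already carry most of that information. At R² of 0.05 to 0.10 the gain is only 1 to 2 points, and at zero adjustment loses 1 to 2. This stands, and it makes the gain conditional.

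**The error is on the safe side.** It creates no bias and no excess false positives, and it touches only secondary outcomes in a phase II trial. This also stands and limits the weight of the point.

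**A statistical analysis plan could add covariates.** It could, but section 9.2 names a covariate set and calls the model equivalent to ANCOVA. A plan that follows it as written would leave the factors out.

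**A stronger reading to avoid.** A reader might infer that every secondary analysis, continuous and categorical, ignores all four factors. The protocol does not support that. The adjusted logistic regression includes all four, Mantel-Haenszel adjusted relative risks are planned, and the eGFR slope model carries some of the factors. For binary outcomes, all that can be said is that an unadjusted test and an adjusted analysis stand side by side with no stated priority.

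Nor does it follow that the chi-square or Fisher test should give way to a Cochran-Mantel-Haenszel test over all 16 strata, at about 3 patients per stratum. In a check assuming response rates of 15% and 50%, with factors that are not prognostic, power was 80% for chi-square, 74% for Fisher and 73% for the 16-stratum test. With a log-odds of 1.0 per factor it was 69%, 63% and 67%.

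**Conclusion.** The point holds for the general ANCOVA and multilevel models of continuous secondary outcomes, excluding the eGFR slope. Stratification is built into the design, and these models do not use it. If the factors are prognostic beyond baseline, the tests are conservative and the intervals too wide. Across the simulations the power lost is 1 to 2 points at R² = 0.10, 4 to 6 at 0.20 and 9 to 10 at 0.30; type I error at R² = 0.30 falls to about 3%. If the factors explain nothing, there is no loss.

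The sizes rest on assumed prevalences, an assumed effect of 0.8 SD and an assumed R². The direction does not depend on the exact values, provided the factors are prognostic. This is a cheap gain in efficiency and does not threaten the validity of the trial's conclusions.

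**What to change.** In section 9.2, add diabetes, obesity, fibrosis stage and CKD, with the binary codings of section 5.5, as main effects in the ANCOVA and multilevel models for continuous secondary outcomes. Do this before unblinding. Apply the same set to every outcome under the general model, so that no covariate is chosen after the data are seen.

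The cost is one sentence of text and 4 degrees of freedom. All four values are known at randomisation, so no new data are needed. The downside is about 1 to 2 points of power if the factors explain nothing.

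For binary secondary outcomes, no new test is needed. At most, name the adjusted analysis already planned as the main one and say which outcomes it covers.
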